## Research Methods

### Outcome Measure(s):

Primary Outcomes: Melatonin phase assessment and IR

Melatonin phase assessment: During the study visit, subjects will be admitted to the Children's Hospital Clinical research center inpatient unit at 4PM on Wednesday, Thursday or Friday. The profile of melatonin release will be assessed at the study visit using a serial saliva sampling method from 5PM on Thursday or Friday to 12PM the following day. Saliva (~2mL) will be collected in 30 or 60 minute intervals in dim light (<10 lux in the room; ~1.9 lux in the angle of gaze, confirmed by light meter) using polystyrene tubes throughout the night. Individualized melatonin sampling schedules will be determined to optimize calculation of DLMOOn and DLMOOff times by introducing 30 minute sampling at the times at which DLMOOn and DLMOOff are predicted to occur based on actigraphy-reported sleep, wake, and midsleep times.

Assessment of IR: During the screening visit, a 3-hour frequently sampled OGTT will be performed in the outpatient CTRC. The OGTT will take place in the AM, after a fast of at least 10 hours. A 20-gauge iv catheter will be inserted in the antecubital vein for blood sampling. After baseline samples are collected, a 3-hour OGTT with 75 mg dextrose drink will be performed. Glucose and insulin samples will be collected every 30 minutes. In addition, we will assess fasting labs to check for other components of metabolic syndrome including hemoglobin A1C for dysglycemia, ALT/AST for liver inflammation, sex hormone binding globulin as a marker of IR, cholesterol panel, CRP as a marker of inflammation, leptin as a gut hormone known to influence hepatic IR, and adiponectin, thought to influence adipose IR. Additionally, blood pressure will be taken to assess for hypertension and waist/hip ratio will be measured as a marker of metabolic disease.

Additional Measures: Questionnaires assessing additional sleep parameters, mood/behavior, and diet/activity will be completed by participants to identify variables to control for in analyses (e.g. presence of symptoms of sleep-disordered breathing) and/or utilize in exploratory analyses (e.g., relationship between sleep and diet/activity).

- i. The **Morningness/Eveningness Scale for Children**  and the **Munich Chronotype Questionnaire for Children**  will be used to determine chronotype (diurnal preference).

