- ii. The **Cleveland Adolescent Sleepiness Questionnaire**, **Sleep Disturbances Scale for Children/Adolescents**, and the **Adolescent Sleep Hygiene Scale** will be completed by participants to obtain information on behavioral sleep variables, including daytime sleepiness and sleep-promoting and inhibiting factors.
- iii. The **Strengths & Difficulties Questionnaire**, an adolescent self-report tool, will be used to assess symptoms of mood and behavior problems.
- iv. The **Profile of Mood States 2 Short Version**, an adolescent self-report measure of mood, completed on the computer.
- v. The **Three Day Physical Activity Recall** (3DPAR^10), a questionnaire asking youth to recall their physical activity levels from the previous three days, will be completed. Physical activity can directly affect insulin sensitivity, our primary outcome measure.
- vi. Macronutrient intake pattern will be ascertained using the **SEARCH Food Frequency Questionnaire**, devised to include common food choices among ethnically and regionally diverse youth aged 10-19 years. The instrument is self-administered with staff support to provide instructions, answer questions, and to review the form after completion, and captures the last week of dietary intake.
- vii. Psychomotor Vigilance Task, a computerized test of sustained attention with particular sensitivity to sleepiness.

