**viii. Description of Population to be Enrolled:**

Participants: This pilot study would allow for preliminary data collection on up to 30 obese adolescents (15 male, 15 female).

Recruitment: Participants will be recruited from adolescent, obesity and community clinics.

Subject Criteria:

*Inclusion criteria:*

- 1) High school students between the age of 15-19 years (the peak developmental period for delayed circadian phase);
- 2) BMI >90th percentile for age and sex;
- 3) Tanner stage 2 or greater.

*Exclusion criteria:*

- 1) Any medications that affect IR or sleep (e.g., metformin, hormonal contraception, stimulants, atypical antipsychotics);
- 2) regular use of melatonin or other sleep aids;
- 3) a prior diagnosis of obstructive sleep apnea, diabetes (HbA1c > 6.5), liver disease other than non-alcoholic fatty liver disease, pregnancy or breastfeeding;
- 4) IQ<70 or severe mental illness that may impact sleep (e.g., schizophrenia, psychotic episodes), verified through chart review;
- 5) teens not enrolled in a traditional high school academic program (e.g., home school students);
- 6) night shift employment;
- 7) travel across more than two time zones in the month prior to the study.

Informed Consent Plan: Appropriately qualified and informed personnel who have completed the COMIRB and HIPPA course requirements will fully explain the study protocol and consent form to the subject and guardian verbally in the language they understand. The explanation will be conducted in a quiet environment with adequate time given for the subject and guardian to review the study procedure before the commencement of the study. Asking the subject to explain the study in their own words will assess the subject's understanding. If non-English speaking subjects are enrolled in the study, the investigators will adhere to Section 10C of the COMIRB Instructions for Clinical Investigators regarding the consent of these subjects. The qualified personnel mentioned above will then obtain written consent from the guardian and assent from the subject, co-signed on the consent form, or in subjects who are 18 years or older, direct consent. The PI will make a good faith effort to obtain both parent signatures. The subject and guardian will be provided a copy of the consent form for better understanding and record purposes.

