## **Data Analysis Plan:**

**Aim 1 Analysis Plan:** Demographic and clinical characteristics will be summarized by group with descriptive statistics. Prior to analysis, variables will be examined for unusual values for query, missing data, and whether distributions are non-normal, in which case a transformation may be applied.

**Melatonin modeling:** The timing of melatonin onset and offset will be computed according to standard procedures that have been validated in adolescents . We will define DLMO phase as the clock time

at which evening salivary melatonin concentrations increase and remain above a 4pg/mL threshold using linear interpolation between successive samples . Similarly, we will define DLMOff phase as the clock time at which salivary melatonin concentrations fall below this threshold. Phase angles of entrainment will be computed as the time interval between DLMO and average actigraphic estimates of sleep variables, including bedtime, mid-sleep time, and wake time. Additional characterization of the melatonin profile, including assessment of melatonin amplitude, will also be conducted.

Aim 2 Data Modeling Plan: To investigate the relationship between sleep/wake behavior and circadian phase in obese adolescents, we will develop a physiologically-based mathematical model of sleep/wake and circadian interactions that simulates adolescent sleep patterns. Model equations will be implemented in MATLAB and solved numerically using an appropriate solver. Initially, we will fit model behavior to published characterizations of adolescent sleep/wake behavior. After establishing a representative model of adolescent sleep, we will assess the role of key model parameters in the production of key elements of adolescent sleep, and we will investigate the role of these parameters in inter-individual differences observed in sleep/wake behavior in study participants as characterized by actigraphy data.

Aim 3 Calculations and Data Analysis Plan:

*Power calculation:* A sample size of 30 participants will provide 80% power to detect a correlation coefficient equal to 0.47, given a 2-sided  $\alpha=0.05$ . Because this is a pilot study, even if the null hypothesis is not rejected, the information gained regarding possible effect sizes will be useful in obtaining subsequent extramural funding for additional participants and in planning a larger study.

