*Calculation of insulin resistance:* IR will be calculated with the Matsuda Index, a composite model for insulin sensitivity which accounts for changes in both the insulin and glucose concentrations over time . The value derived from this equation is an M value of glucose uptake in mg/m^2/min, which is approximated to results that would likely have been obtained if a more invasive hyperinsulinemic-euglycemic clamp test had been performed . The range of values is 0–14, with 14 being the highest level of insulin sensitivity and zero the lowest. Additional exploratory measures including B-cell function [insulinogenic index ( $\Delta I30/\Delta G30$ ) and ( $\Delta C30/\Delta G30$ ) and disposition index ( $1/I\text{Fasting} \times \Delta I30/\Delta G30$ ) and ( $1/C\text{Fasting} \times \Delta C30/\Delta G30$ ) will also be calculated .

*Relationship between circadian phase and IR:* DLMO and DLMOff will be determined from the measures of salivary melatonin concentrations as described above. Each subject will have one DLMO time and one DLMOff time. The relationship between DLMO and DLMOff and IR will be assessed by comparing DLMO and DLMOff to the whole body Matsuda index using correlation and linear models. All models will have melatonin onset or offset as the outcome, and gender effects will be considered. The relationship between average actigraphy-estimated sleep duration (from sleep watch) and IR will also be tested using correlation and linear models.

3. Roenneberg T. Munich Chronotype Questionnaire. n.d.; <http://www.imp.med.uni-muenchen.de/index.html>. Accessed February 18, 2015.

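### Must the Aim 3 models name covariates beyond gender before the phase–insulin resistance analysis can be trusted?

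*Combined protocol and SAP*

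**What the plan says.** The Aim 3 analysis plan (paragraph on circadian phase and IR) compares DLMO and DLMOff with the Matsuda index by correlation and linear models. It then states: "All models will have melatonin onset or offset as the outcome, and gender effects will be considered". The next sentence reads: "The relationship between average actigraphy-estimated sleep duration (from sleep watch) and IR will also be tested using correlation and linear models". No covariate list or selection rule appears anywhere.

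Other sections bear on the choice of covariates:

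- Outcome Measure(s), Additional Measures, says the questionnaires serve "to identify variables to control for in analyses (e.g. presence of symptoms of sleep-disordered breathing" and similar), and/or for exploratory analyses.
- The physical activity item there adds: "Physical activity can directly affect insulin sensitivity, our primary outcome measure".
- The inclusion criteria justify ages 15–19 as "the peak developmental period for delayed circadian phase", and admit "Tanner stage 2 or greater" and BMI above the 90th percentile.
- The power statement reads: "A sample size of 30 participants will provide 80% power to detect a correlation coefficient equal to 0.47".
- The outcome heading reads "Primary Outcomes: Melatonin phase assessment and IR". The activity item and the Blood Sampling justification each attach the primary label to insulin sensitivity or IR alone.

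**The concern.** A factor that shifts both melatonin timing and insulin sensitivity can create an association where none exists, or hide a real one. A model with gender alone does not remove it. The protocol says it will look for control variables, says activity affects insulin sensitivity and ties the age band to circadian phase, yet none of these variables is named in the models. The pilot's effect sizes are meant to support funding and the design of a larger study, so a confounded estimate would carry forward. Leaving the adjustment set open with 30 participants also allows it to be chosen after the results are seen.

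Three wording points add to the impression. The sleep-duration model has no melatonin variable, so a rule for all models cannot cover it. Considering gender effects could mean a main effect or an interaction. The primary outcome is labelled in more than one way.

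**Working it through.** **1. The plan's own figure.** Inputs from the power paragraph: n = 30, r = 0.47, two-sided α = 0.05. For a one-predictor regression slope, the noncentrality is √30 × 0.47/√(1 − 0.47²) = 2.92 on 28 degrees of freedom, which gives power 0.804. The stated 80% reproduces and refers to an unadjusted association.

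**2. What unmeasured adjustment could cost.** The documents give no correlation between any covariate and phase or IR, so all inputs here are assumed. Let a covariate correlate a with phase and b with IR, with no direct link between the two. The crude correlation is then a × b. Simulated false rejection at n = 30, 15 per sex:

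| a | b | crude r = ab | crude test | gender-only model | sex, true confounder and age |
|---|---|---|---|---|---|
| 0.1 | 0.5 | 0.05 | 5.8% | – | – |
| 0.2 | 0.4 | 0.08 | 6.9% | 6.9% | 4.9% |
| 0.3 | 0.5 | 0.15 | 12.2% | 11.9% | 4.9% |
| 0.4 | 0.6 | 0.24 | 25.2% | 24.5% | 5.1% |

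At a = 0 the crude rate is the nominal 5%.

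Masking is also possible. With a true partial r of −0.47 and a = 0.3, b = 0.5, the crude r is −0.47 × √(0.91 × 0.75) + 0.15 = −0.24. The gender-only model then detects the association 24% of the time, and the model with the true confounder 72%.

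**3. Whether a listed set would cure it.** The last column assumes that the adjusted model holds the real confounder, measured without error. If that variable is left out of a three-covariate model, false rejection at a = 0.3, b = 0.5 is about 11%, close to the crude 12.2%. If it is included with an assumed reliability of 0.5, the rate is about 7% (10.4% at 0.4 and 0.6). Naming a list therefore helps only if it is the right list.

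**4. Whether the documents identify the right list.** A confounder must affect both sides.

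- Activity is tied to insulin sensitivity, not to phase.
- The age band is tied to phase. The text does not say that phase varies within 15–19, or that age affects IR.
- BMI and Tanner stage are tied to neither in the eligibility text.
- Menstrual timing is tied to IR only, and is handled by follicular-phase scheduling when possible.

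Several influences are limited by design: the age band, exclusion of diagnosed sleep apnea and of drugs affecting IR or sleep, and data collection in the academic year.

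**5. Cost of adjusting.** On the basis used in step 1, taking the effective sample size as n less the number of covariates, power at a partial r of 0.47 is 0.758 with three covariates and 0.722 with five. The Fisher-z half-width goes from 1.96/√27 = 0.377 to 1.96/√24 = 0.400 with three covariates, 6% wider. Adjustment is affordable, so cost is not the reason for leaving the plan alone.

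**6. The wording points.** With the same covariates, the phase–IR association p-value is the same whichever variable is the outcome; the largest difference over 300 simulated data sets was 7 × 10⁻¹⁶. This does not extend to a sex-by-IR interaction. That term could only be exploratory here in any case. Comparing two correlations with 15 per sex has standard error √(2/12) = 0.408, so 80% power needs a Fisher-z difference of 2.80 × 0.408 = 1.14, roughly r = 0 against r = 0.82. This is a guide only, since an interaction term compares slopes.

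**The case for a change.** The strongest case for a change is that the effect estimate is this pilot's main product. The protocol collects variables for control and never says which will be used, and a few sentences would close the gap with no new data. Crude correlations would remain the powered analysis, with adjusted slopes beside them.

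Part of this stands. The list is missing, gender effects are not defined, and naming covariates in advance is good practice that would limit selective choice.

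The case for requiring it is weaker. The questionnaire passage states an intention to control for variables, so silence in the model paragraph does not mean gender only. Any particular set is debatable. BMI may lie on the pathway, so adjusting for it could remove part of the association of interest. A main model of sex, BMI and age would leave out the protocol's one named example, sleep-disordered-breathing symptoms, as well as Tanner stage and menstrual timing. Keeping the crude correlation as the main test would also leave its false-rejection rate where it was.

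**Conclusion.** No change follows. The missing covariate list is a detail that analysts can fill from the variables the protocol already says it will examine for control. The documents make confounding possible but do not show it. Under the assumed correlations, false rejection by the crude test lies between about 5% and 25%. The improvement from adjustment depends on knowing the confounder and measuring it well, which the documents cannot settle.

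The outcome rule is naturally read as covering the DLMO and DLMOff models of the sentence before it. The sleep-duration analysis can stand on its own terms. The outcome heading names both phase and IR as primary, so the passages that call IR primary are loose rather than contradictory. None of these points alters an association test or the reproduced power of 0.804. Because the study is a pilot, its correlations should be read as unadjusted, preliminary estimates when the larger study is planned.
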